m Patients must fast (water to drink only) for at least 2 hours prior to taking a dose to at least 1-hour post-dose for all doses

n CT (preferred) or MRI, each preferably with IV contrast. It is strongly recommended to maintain use of the same imaging modality (CT or MRI), acquisition protocol, facility and scanner across all imaging time points per patient.

o 480 mg IV infusion over 60 minutes, q4w +/- 3 days, unless an infusion needs to be held due to an adverse event. Results for vital signs (including weight), performance status, chemistry, haematology and thyroid function labs must be available before commencing an infusion (within 3 days) and reviewed by the treating physician or Investigator prior to dosing

p Survival and details of first and subsequent therapies for cancer, after discontinuation of treatment, will be collected.

q Patients treated with RXC004 monotherapy that radiologically progress as per RECIST1.1 at the 8 week scan, may be treated with RXC004 + nivolumab combination, subject to meeting combination treatment eligibility criteria. The most recent scan that shows progression on RXC004 monotherapy treatment will be used as the baseline scan for the combination treatment (see Section 7.1.1 and Appendix D for more details).

r Height is required at screening only

s CCI

CCI

t CCI

CCI

CCI

CCI

CCI

CCI

u T3 and T4 will only be measured if TSH is abnormal or if there is clinical suspicion of an AE related to the endocrine system

v Follow up assessments should be performed 30 days after discontinuation of RXC004 and 90 days after last dose of nivolumab (for patients treated with RXC004 and nivolumab)

w A dental examination with preventive dentistry if appropriate and an individual benefit-risk assessment is mandatory prior to treatment with denosumab. An initial dental examination may be performed by a member of the clinical team who can assess the need for referral to a dentist for further assessment including any preventative dentistry. A visual oral examination (including tongue, palate, uvula, tonsils, buccal mucosa, lips, gums and parotid duct) should also be performed at baseline and at each scheduled visit where dysgeusia is reported as an adverse event.

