\*\*~~CCI~~ [REDACTED], ideally from the same site of disease (e.g. liver, lymph node etc) that the 'on treatment' biopsy will be taken from, and taken after completion of all prior standard of care treatments will be accepted as a baseline biopsy.

- 8 Patients with adequate organ functions as described below;
  - AST/ALT  $\leq$  2.5X ULN (upper limit of normal) [with no underlying Liver Metastasis]
  - AST/ALT  $\leq$  5 X ULN [with underlying Liver Metastasis]
  - Total Bilirubin  $\leq$  1.5 X ULN
  - Serum Creatinine  $\leq$  1.5 X ULN
  - ANC  $\geq$  1.5  $\times$  10^9/L
  - Platelets  $>$  100  $\times$  10^9/L
  - Hb  $>$  8.5g/dL (with or without transfusional support)
  - Calculated creatinine clearance (CrCL)  $\geq$  60 mL/min as determined by Cockcroft Gault (using actual body weight).

Males:

$$\text{CrCL} = \frac{\text{Weight (kg)} \times (140 - \text{Age})}{72 \times \text{serum creatinine (mg/dL)}}$$

Females:

$$\text{CrCL} = \frac{\text{Weight (kg)} \times (140 - \text{Age})}{72 \times \text{serum creatinine (mg/dL)}} \times 0.85$$

- 9 Female patients of childbearing potential must have a negative pregnancy test prior to start of dosing
- 10 Female patients of childbearing potential and male patients with female partners of childbearing potential must agree to use a highly effective method of contraception during the study and for at least 5 months after the last dose of study drug. See Section 5.3.1 for details of acceptable methods of contraception

**For patients on RXC004 monotherapy treatment (Arm A) the following inclusion criteria will also apply to enter the RXC004 + nivolumab treatment phase;**

11. Patients must have had documented RECIST1.1 defined radiological progression on RXC004 monotherapy treatment on the first scheduled scan (week 8 +/- 1 week)
12. Patients must receive Cycle 1 Day 1 of combination study treatment within 28 days of the first scheduled scan (week 8 +/- 1 week) showing RECIST1.1 defined radiological progression, or for clinically stable patients that remain on RXC004 after RECIST1.1 defined radiological progression, within 28 days of the most recent scan showing further radiological progression or confirmation of the week 8 RECIST1.1 progression (see Section 7.1.1 and Appendix D for more details)

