### **7.1.1 Treatment of Symptomatically Stable Patients after RECIST 1.1 Defined Progression**

Patients with symptomatically stable disease may continue treatment after the initial RECIST 1.1 – defined progression, until symptomatic/clinical progression or a second RECIST 1.1 PD assessment (relative to the initial RECIST1.1 progression, for a given study treatment).

Patients who wish to continue study treatment after RECIST1.1 defined progression, should be informed of all other alternative treatment options available to them by the treating physician and sign an additional consent that they wish to continue study treatment. A decision to continue study treatment after initial progression must also be discussed and agreed by the treating physician and the Sponsor.

The criteria for continuing treatment after initial RECIST 1.1-defined progression are as follows:

- Signed patient consent for treatment after progression
- The patient does not have any significant, unacceptable, or irreversible toxicities indicating that continuing treatment will not further harm the patient.

- There is absence of clinical symptoms or signs indicating clinically significant disease progression accompanied by a decline in ECOG performance status >1.
- There is absence of rapid disease progression or threat to vital organs or critical anatomical sites (e.g. central nervous system metastasis, respiratory failure due to tumour compression, or spinal cord compression) requiring urgent alternative medical intervention.
- Study treatment was not on hold/interrupted at time of progression

Patients continuing study treatment after initial RECIST 1.1 defined progression should continue RECIST scans as per the Schedule of Assessments (the next tumour assessment should be at least 4 weeks after the first RECIST 1.1 defined progression and no later than the next regularly scheduled imaging timepoint).

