## Treatment after first progression (Arm B)

TL – Target Lesion, NTL – Non-Target Lesion, NL New Lesion

**Figure 4** Treatment after first progression for patients that remain on RXC004 monotherapy (Arm A)

\* Subject to RXC004+Nivolumab recruitment being open and combination eligibility criteria being met. The most recent progression scan will become the RXC004 + Nivolumab baseline scan

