4.2.3 Definition of Baseline and Post-baseline Assessments

A baseline assessment will be defined as the last assessment performed prior to the first dose of study treatment (C0D1). While many of these assessments will be performed on the day of the first dose, others will be performed during screening. If a patient is missing an assessment typically performed on the day of the first dose, screening values may be substituted as baseline.

Patients treated with RXC004 monotherapy (arm A) that radiologically progress as per RECIST1.1 at the first 'on treatment' scan, may be treated with RXC004 + Nivolumab combination. Accordingly, the following groups of analyses have to be defined to clarify which patients and which information in arm A will be utilized:

- **Arm A (RXC004 monotherapy):** this group will include information for all patients enrolled in arm A.
- **Arm A1 (RXC004 monotherapy):** this group will include information of all patients enrolled in Arm A who were on monotherapy throughout the study - ie. subjects who did not radiologically progressed at the first scan (week 8) or who radiologically progressed

at the first scan (week 8) but remained on monotherapy or who withdrew before the first scan.

- **Arm A2 (RXC004 + Nivolumab):** this group will include information of patients enrolled in arm A who radiologically progressed at the first scan (Week 8) and then switch to receive combination therapy of RXC004 + Nivolumab either at Week 8 or later. The last scan before the switch to combination treatment will be set as the arm A2 baseline RECIST1.1 scan for the combination treatment. The date of the last scan before switching to combination treatment will also be used to determine the arm A2 baseline date for all the efficacy endpoints except OS. OS will keep the same baseline regardless of the progression. For assessments other than efficacy, Arm A2 summaries, will include data from start of monotherapy until end of combination treatment.
- **Arm B (RXC004 + Nivolumab):** this group will include information on all patients enrolled in arm B.

Some patients with symptomatically stable disease may continue treatment after the initial RECIST 1.1 - defined progression, until symptomatic/clinical progression or a second RECIST 1.1 PD assessment (relative to the initial RECIST1.1 progression, for a given study treatment).

Change from baseline is derived where both baseline and post-baseline values are available:

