4.11.3.1 Percentage change in sum of target lesions

The % change in sum of target lesions is defined in Section [3.2.1.4](#) .

Percentage change in tumour size will be derived at each visit by the percentage change from baseline in the sum of diameters of target lesions will be provided for arm A and arm B. It will also be summarized for arm A2.

In arm A and arm B, % change in sum of target lesions will be always computed considering screening sum of diameters as baseline. For patients in cluster arm A2, % change in sum of target lesion will be computed considering as reference the sum of diameters computed at Week 8. In case some individual lesions are not measured, the whole sum of target lesions will be considered as missing.

Percentage change in tumour size will be listed per visit for all patients in FAS.

The best percentage change in tumour size will be the patients value representing the largest decrease (or smallest increase) from baseline in tumour size.

A waterfall-plot will be produced to report the best % change in sum of target lesions for each patient (considering the minimum observed value) ordered by largest increase to greatest decrease. In addition, two waterfall-plot will be produced to report the % change in sum of target lesions at Week 8 and Week 16. Best overall responses (BOR) will be highlighted for each patient. The figure will be repeated considering RNF43 and RSPO2/3 Status instead of BOR.

A Spider-plot will be drawn to describe the % change in sum of target lesion. Vertical axis will represent the % change in sum of target lesions (% change in tumour size) while the horizontal axis will represent days from screening, as follows:

day (x-axis) = date of RECIST 1.1 assessment – first dose of study treatment (C0D1)

Best overall responses (BOR) will be highlighted for each patient. The figure will be repeated considering RNF43 and RSPO2/3 Status instead of BOR.

All plots will be provided for the FAS separately for arm A, arm A2 and arm B. The spider plot for A2 will still use the original baseline to week 8 so it is clear what the changes were when the patient switched to the combination.

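### SAP 4.11.3.1 measures Arm A2 tumour change from the Week 8 sum, but SAP 4.2.3 and the protocol take a later scan as baseline for patients who switch late

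*SAP*

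**What the plan says.** SAP 4.11.3.1 uses the screening sum as baseline for Arms A and B. For Arm A2 the percentage "change in sum of target lesion will be computed considering as reference the sum of diameters computed at Week 8". Best change is the minimum observed value and is shown in a waterfall plot. One sentence keeps the original baseline for the A2 spider plot as far as Week 8, so that the change at the switch can be seen.

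SAP 4.2.3 has a different rule for the same group: "The last scan before the switch to combination treatment will be set as the arm A2 baseline RECIST1.1 scan for the combination treatment". It applies the date of that scan to all efficacy endpoints except OS. It also describes A2 as patients who progressed at the first scan and then "switch to receive combination therapy of RXC004 + Nivolumab either at Week 8 or later".

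The protocol agrees with SAP 4.2.3 in substance:
- Table 1, footnote q: "The most recent scan that shows progression on RXC004 monotherapy treatment will be used as the baseline scan for the combination treatment".
- Appendix D, note to Figure 4: "The most recent progression scan will become the RXC004 + Nivolumab baseline scan".
- Inclusion criterion 12 (Section 5.1) lets a clinically stable patient stay on monotherapy after Week 8 progression and start the combination "within 28 days of the most recent scan showing further radiological progression or confirmation of the week 8 RECIST1.1 progression".

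**The concern.** If every switch followed directly from the Week 8 scan, the two SAP rules would give the same number. They do not for a patient who stays on monotherapy, has a further scan, and then switches. Section 4.11.3.1 then divides by the Week 8 sum, while 4.2.3 divides by the later sum. Under 4.11.3.1, any change between Week 8 and the switch happened on monotherapy but is counted as change on the combination.

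There is a second consequence. With Week 8 as the reference, nothing in 4.11.3.1 stops a scan taken after Week 8 but before the switch from supplying the A2 best value. A monotherapy measurement could then stand as the best result on the combination.

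At stake is how the sequential-combination group reads in the percentage-change summary and waterfall plots, which are outputs where the eye goes to the −30% line.

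**Working it through.** The plan states no figure to reproduce. The check sets the two rules side by side and works out how far apart they can be.

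**When the rules differ.** They agree if the last pre-switch scan is the Week 8 scan, or if the sum did not change between the two scans. Otherwise they differ. Protocol 7.1.1 says the next assessment after first progression "should be at least 4 weeks after the first RECIST 1.1 defined progression and no later than the next regularly scheduled imaging timepoint", so a late switcher's two scans are at least 4 weeks apart.

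**Formula.** Let g be the change in the target-lesion sum from Week 8 to the last pre-switch scan, and c the change from that scan to a later one. Then

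change against Week 8 = (1 + g)(1 + c) − 1.

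**Inputs.** The documents give no values for g, so those below are assumptions. c = −30% is the PR size threshold in Appendix D.

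| Assumed g | Change by the 4.2.3 baseline (c) | Change by the Week 8 sum |
|---|---|---|
| −10% | −30% | 0.90 × 0.70 − 1 = −37% |
| 0 | −30% | 1.00 × 0.70 − 1 = −30% |
| +10% | −30% | 1.10 × 0.70 − 1 = −23% |
| +20% | −30% | 1.20 × 0.70 − 1 = −16% |
| +30% | −30% | 1.30 × 0.70 − 1 = −9% |

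In millimetres (assumed sums): Week 8 sum 100, last pre-switch sum 120, on combination 84. By 4.2.3 the change is (84 − 120)/120 = −30%. By 4.11.3.1 it is (84 − 100)/100 = −16%. With g = +20%, a fall of 1 − 0.70/1.20 = 41.7% from the pre-switch scan is needed before the Week 8 calculation shows −30%. With g = −10%, a fall of 1 − 0.70/0.90 = 22.2% is enough.

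**Which values of g are plausible.** Protocol 7.1.1 judges second progression relative to the first, and Appendix D requires at least a 20% increase in the sum for target-lesion PD. A late switcher who progresses again on target lesions would therefore have g of about +20% or more. Criterion 12 also admits patients whose later scan only confirms the Week 8 progression; g may then be near 0. Progression can also come from new or non-target lesions (Appendix D; SAP Table 3), so the target sum may fall and g may be negative.

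**The best-change problem.** Assume a Week 8 sum of 100 mm, a pre-switch scan at 90 mm with progression through a new lesion, and a lowest combination value of 95 mm. Read literally, 4.11.3.1 could report (90 − 100)/100 = −10%, taken from the monotherapy scan. By 4.2.3 the best change on the combination is (95 − 90)/90 = +5.6%.

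**What is not touched.** SAP 3.2.1.1 derives BOR only from the overall response that the investigator records, and ORR and DCR follow from BOR. The percentage-change calculation does not enter Arm A DCR, Arm B ORR or A2 ORR.

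**The case against.** The best defence is that 4.2.3 is the general rule. It covers all efficacy endpoints except OS and foresees late switching, so the Week 8 wording in 4.11.3.1 is probably shorthand that was not updated. That is likely, and it limits the weight of the point. It does not remove it: 4.11.3.1 is the section that specifies these outputs, it names a particular scan, and neither section says which takes precedence.

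It can also be said that waterfall bars and BOR labels often disagree anyway, because responses need confirmation and new lesions override target shrinkage. The SAP does not say whether the A2 plot carries the A2 BOR either. Both remarks are fair. The point therefore rests on the denominator, not on a mismatch with the label.

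Three stronger readings are tempting, and the documents do not support them.
- A reader might infer that the Week 8 reference always understates the combination. It does so when g is positive; when g is negative it overstates.
- A reader might infer that the primary results are compromised. They come from investigator-recorded responses and are not affected.
- A reader might infer that the safety analysis is also wrong, because SAP 4.2.3 lets A2 non-efficacy summaries run from the start of monotherapy to the end of combination. Protocol 9.4.3 deliberately reports safety by initial treatment, with some outputs split between monotherapy-only patients and switchers, and SAP 4.12.1 and 6.2 follow that. Extra tables cut at the switch would be a preference. A related worry is that visit windows might overlay the two phases. This needs the less natural reading of SAP 4.2.2, which chooses C1D1 because of delays after C0D1; only the monotherapy sequence in Arm A has a Cycle 0.

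**Conclusion.** SAP 4.11.3.1 is wrong as written, with limited reach. It contradicts SAP 4.2.3 and the protocol for patients who switch after a post-Week 8 scan. For a patient at −30% on the combination, the reported value would lie between −37% and −9% over assumed g of −10% to +30%. That range is an illustration, because the documents give no lesion data.

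The number of late switchers is not stated; Table 1, footnote j allows up to 20 switchers in all. Only the late switchers' A2 percentage-change summary and waterfall plots are affected. The protocol (9.4.1) asks for separate ORR, DCR and PFS in these patients; A2 percentage change is an addition made by the SAP.

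The A2 spider plot is a stated exception and does not resolve the conflict. Its wording also treats Week 8 as the moment of the switch.

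**What to change.** - In SAP 4.11.3.1, replace the Week 8 sum as the A2 reference with the sum of diameters at the A2 baseline scan defined in Section 4.2.3.
- State that only scans after the switch count towards A2 best change.
- Use one wording for the A2 baseline scan in both documents. The SAP's last scan before the switch and the protocol's most recent scan showing progression normally coincide, but they could differ if the last scan does not itself show progression.
- For the A2 spider plot, say that the original screening baseline is used throughout and mark the switch date, in place of the limit at Week 8.
- Optional: one sentence in SAP 4.2.2 saying which C1D1 drives the visit windows of switchers.

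The cost is a few phrase edits. No new data are needed: SAP 4.10.1 already calculates RXC004 dose intensity from the start of the combination, so the switch date is available.

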4.11.3.2 Progression Free Survival (PFS)

PFS is defined in Section [3.2.1.5](#).

Kaplan-Meier analyses will be conducted for arm A and arm B (in the same plot) and separately for arm A2. For arm A, the patients who switched due to progression at first scan will be considered as having progressed. Survival plots will be produced to present Kaplan-Meier estimated curves. In

addition, the following parameters estimated from the Kaplan-Meier curves will be provided for each group:

- median PFS and corresponding 95% CIs
- PFS rate at 3, 6 and 12 months and corresponding 95% CIs (one month = 30.4375 days).

PFS will be listed for all patients in the FAS.

4.11.3.3 Overall Survival

OS is defined in Section [3.2.1.6](#).

Kaplan-Meier analyses will be conducted for arm A and arm B (in the same plot) and separately for arm A2. Survival plots will be produced to present Kaplan-Meier estimated curves.

OS will be listed for all patients in the FAS.

4.11.4 Pharmacokinetics/Pharmacodynamic

CCI

4.12 Safety Evaluation

Safety summaries and analyses will be based on the FAS.

4.12.1 Adverse Events

Adverse Events will be collected from time of signature of informed consent form throughout the treatment period and until 30 days after the last dose of RXC004 (for patients treated with RXC004 monotherapy only) or 90 days after the last dose of Nivolumab (for patients treated with RXC004 and Nivolumab).

SAEs will be recorded from the time of signing of informed consent form until the follow-up period is completed: 30 days after the last dose of RXC004 (for patients treated with RXC004 monotherapy only) or 90 days after the last dose of Nivolumab (for patients treated with RXC004 and Nivolumab).

The following variables will be collected for each AE:

- AE (verbatim)
- Start/Stop date
- CTCAE grade at onset and grade changes
- Seriousness
- Investigator causality rating against the Investigational Product(s)
- Action taken with regard to Investigational Product(s)
- Action taken with regards to AE

- Outcome

In addition, the following variables will be collected for SAEs:

- Date AE met criteria for SAE
- Date investigator became aware of SAE
- Hospitalisation
- Life Threatening
- Congenital Anomaly or Birth Defect
- Disability or Permanent Damage
- Other Medically Important Serious Event
- Date of hospitalisation
- Date of discharge
- Causality assessment in relation to Study procedure(s)
- Causality assessment to other medication

Partially complete AE dates will not be imputed in the listings and the available day, month and year components will be used to determine if an adverse event is treatment- emergent taking the first dosing date last treatment date as references.

More specifically:

- Start date of AE missing: Assumed to be date of first treatment dose.
- Start day and month of AE missing: Assumed to be date of first treatment dose (if same year for both dates), January 1st otherwise.
- Start day of AE missing: Assumed to be date of first treatment dose (if same month and year for both dates), first day of the month otherwise.
- End date for non-ongoing AE missing: Assumed to date of last treatment dose
- End day and month for non-ongoing AE missing: Assumed to be date of last treatment dose (if same year for both dates), December 31st otherwise.
- End day for non-ongoing AE missing: Assumed to be date of last treatment dose (if same month and year for both dates), last day of the month otherwise.

Explain if first use TEAEs with missing relationship to the study drug will be considered as related. AEs will be coded using the MedDRA, latest version. Grading will be performed using CTCAE version 5.0.

TEAEs are defined as those AEs with an onset after dosing and those pre-existing AEs that worsen after the start of dosing and within 30 days of stopping RXC004 monotherapy or 90 days after the last actual Nivolumab dose (for patients on RXC004 and Nivolumab combination).

An overview table of TEAEs will be provided showing the number of patients, the percentage of patients and the number of events for the following categories of events:

- Any TEAE
- Any treatment related TEAE to RXC004
- Any treatment related TEAE to Nivolumab
- Any grade ≥ 3 TEAE
- Any grade ≥ 3 TEAE related to RXC004
- Any grade ≥ 3 TEAE related to Nivolumab
- Any serious TEAE (STEAE)
- Any serious TEAE related to RXC004
- Any serious TEAE related to Nivolumab
- Any TEAE leading to death
- Any TEAE leading to permanent discontinuation or reduction or interruption of RXC004
- Any TEAE leading to permanent discontinuation of RXC004
- Any TEAEs leading to RXC004 reduction
- Any TEAEs leading to RXC004 interruption
- Any TEAE leading to permanent discontinuation or interruption of Nivolumab
- Any TEAE leading to permanent discontinuation of Nivolumab
- Any TEAEs leading to Nivolumab interruption

For TEAEs, TEAEs considered related (RXC004 and Nivolumab), STEAEs, STEAEs considered related (RXC004 and Nivolumab), TEAEs leading to study treatment discontinuation, TEAEs leading to RXC004 reduction, TEAEs leading to RXC004 interruption, TEAEs leading to Nivolumab interruption, TEAEs by maximum grade, TEAEs with grade ≥ 3 , TEAEs with grade ≥ 3 related to RXC004, TEAEs with grade ≥ 3 related to Nivolumab, death, detailed tables will be created showing the number of patients who experienced at least one TEAE, the corresponding percentage of patients and the number of events by SOC and PT.

SOC will be sorted by alphabetical order. PTs, within each SOC, will be sorted by descending order of total frequency. In the event of PTs with equal total frequencies, the relevant PTs will be sorted

alphabetically.. In addition, a table summarizing TEAEs by decreasing frequency of Preferred Terms will be produced for all TEAEs and TEAEs related to RXC004/Nivolumab.

A table will also be produced showing the details for every patient that die (death date, cause of death etc...).

Listing of all AEs (including non-treatment-emergent events) will be provided. This listing will be presented, ordered by arm and patient. It will include patient identifier, AE (SOC, PT, and verbatim term), date of onset, date of resolution, duration, maximum grade, seriousness, action taken, outcome and causality. A listing detailing the serious TEAEs will also be produced.

TEAEs summaries will be conducted for arm A and arm B and separately for arm A1 and arm A2 (in the same table) as applicable.

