4.8 Prior and Concomitant Medications

Prior and concomitant medications will be coded using the World Health Organization - Drug Dictionary (WHO-DD) Version March 2023 and will be classified by Anatomical Therapeutic Chemical (ATC) categories. Prior medications will be defined as medications that stopped before the first dose of study drug and will be listed only.

For the purpose of categorizing medications as prior or concomitant, incomplete medication start and stop dates will be imputed as follows:

Missing start dates (where UK, UKN and UNKN indicate unknown or missing day, month and year respectively):

- UK-MMM-YYYY: Assume 01-MMM-YYYY. If the month and year are the same as the first dose of study drug month and year, then assume the date of first dose of study drug;
- UK-UKN-YYYY:
 - If the year is prior to the year of first dose of study drug, assume 01-JUL-YYYY of the collected year. If the end date is before 01-JUL-YYYY, assume the first day of the year.
 - If the year is the same as the first dose of study drug year, then assume the date of first dose of study drug. If the End Date occurs before the first dose of study drug, then assume the first day of the year.
 - If the year is after the first dose of study drug year, then assume the first day of the year.
- UK-UKN- UNKN: Assume date of first dose of study drug. In case end date is before first dose of study drug, assume the first day of the year of the CM end date.

Missing stop dates for concomitant medications data will be handled as follows (where UK, UKN and UNKN indicate unknown or missing day, month and year respectively):

- UK-MMM-YYYY: Assume the last day of the month;
- UK-UKN-YYYY: Assume 31-DEC-YYYY;
- UK-UKN- UNKN: Assume ongoing and leave it missing.

Medications will be categorized as follows:

Medication start and stop dates will be compared to the date of first dose of study medication to allow medications to be classified as either Prior or Concomitant.

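### SAP 4.12.1 sets incomplete AE start dates to the first dose without checking a recorded end date, so some screening events that resolved before dosing would be tabulated as treatment-emergent

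*SAP*

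**What the plan says.** SAP 4.12.1 has three rules for an incomplete AE start date.

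- Day missing: "Start day of AE missing: Assumed to be date of first treatment dose (if same month and year for both dates"). If the known month differs from that of the first dose, the first of the known month is used.
- Day and month missing: "Start day and month of AE missing: Assumed to be date of first treatment dose (if same year for both dates), January 1st otherwise".
- Whole date missing: "Start date of AE missing: Assumed to be date of first treatment dose".

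A lead-in sentence says that whatever parts of the date are known decide treatment emergence, judged against the first and last dosing dates. The section then defines a TEAE by onset, or worsening, after dosing begins. AE collection starts at informed consent (SAP 4.12.1; Protocol 8.3.1), and screening runs from Day -28 to Day -1 (SAP 4.2.1).

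SAP 4.8 treats medications differently. If only the year of the start is known and it matches the year of first dose, the rule adds: "If the End Date occurs before the first dose of study drug, then assume the first day of the year". A similar check applies when the whole start date is missing. The classification text later in 4.8 makes a medication prior whenever partial dates clearly show that it stopped before dosing.

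For end dates of resolved AEs, 4.12.1 says: "End date for non-ongoing AE missing: Assumed to date of last treatment dose". Its rules for partly missing end dates follow the same pattern.

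**The concern.** Defaulting to first dose is a sensible convention when timing is unknown. It is not sensible when a recorded end date already shows that the event was over before dosing, because the derived onset then contradicts the data. Screening events are plausible here: the 28-day window includes a mandatory baseline tumour biopsy. TEAE incidence is the main safety output and serves a secondary objective. In arms planned at about 20 evaluable patients, one wrongly included patient is visible in a table. A reader comparing tables with listings could also find a counted TEAE whose listed end date precedes the first dose.

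**Working it through.** The plan states no figure on this point, so there is none to reproduce. The check applies the written rules to dated cases. An imputed onset on the first-dose day is taken as treatment-emergent, which is evidently what the imputation is for.

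**Step 1: the basic case.** Start UK-MAR, end 5 March, first dose 10 March. The start month and year match the first dose, so the start becomes 10 March. The event is a TEAE that ends 5 days before it begins.

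**Step 2: the other patterns** (assumed first dose 20 March 2023).

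| Recorded start | Recorded end | Imputed start | Result |
|---|---|---|---|
| UK-Mar-2023 | 10 Mar 2023 | 20 Mar 2023 | TEAE; ends 10 days before start |
| UK-UKN-2023 | 10 Mar 2023 | 20 Mar 2023 | TEAE; ends 10 days before start |
| Fully missing | 10 Mar 2023 | 20 Mar 2023 | TEAE; ends 10 days before start |
| Fully missing | 25 Feb 2023 | 20 Mar 2023 | TEAE; ends 23 days before start |
| UK-Feb-2023 | 10 Mar 2023 | 1 Feb 2023 | Not a TEAE; correct |

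**Step 3: how often the rule misfires when it is used.** Take every first-dose day of one calendar year (2023, assumed) and every start/end pair inside a 28-day screening period, equally weighted (assumed). That gives 28 × 29 / 2 = 406 pairs per dose day, and 406 × 365 = 148,190 pairs. The share of these screening-only events that becomes treatment-emergent is:

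- start day missing: about 38% (52% if each start day, rather than each pair, is weighted equally)
- day and month missing: about 95%
- whole start date missing: 100%

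These shares are conditional on the start date being incomplete in that way. They say nothing about how many such records exist. If a known end before first dose rules out treatment emergence, all three fall to 0%.

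**Step 4: size in a table.** One misclassified patient changes a term's incidence by 100/n percentage points. With n = 20 that is 100/20 = 5 points. Safety summaries use the full analysis set (SAP 4.12), which is everyone dosed. SAP 4.14 plans enrolment so that about 20 per arm are evaluable, and the enrolment figure is redacted. For n above 20 the step is below 5 points. It is zero if the patient also has the same term on treatment, because each patient is counted once per term. The separate A1 and A2 columns have smaller denominators, which the documents do not give.

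**Step 5: the medication rules, matched like for like.** The SAP 4.8 rule for a start with only the day missing also goes to first dose without an end-date check, so that rule alone would not rescue the case in Step 1. The override later in 4.8 does, because a known stop before dosing makes the medication prior. SAP 4.12.1 has no counterpart to that override.

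**Step 6: end dates.** With last dose 10 June, a resolved AE that started on 5 July and has no end date is given an end of 10 June, 25 days before its start. AEs are collected for 30 or 90 days after last dose, so this can occur. TEAE status rests on onset, so no TEAE count changes.

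**The case against.** The best defence is the lead-in sentence of 4.12.1. It lets the known date parts decide treatment emergence and does not limit them to start-date parts, so a programmer might use a known end date. That reading is arguable but weak. The sentence names only the first and last dosing dates as references, and the detailed rules that follow contain no end-date check.

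It can also be said that over-counting TEAEs is the conservative direction for safety, that AE listings show unimputed dates, and that SAP 4.1 requires independent checking of outputs. All three are true and limit the harm. None makes the derived status right, and checking against the specification would confirm the rule as written.

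Three stronger readings are tempting, and the documents do not support them.

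- A reader might infer that screening events in general are counted as TEAEs. Only those with an incomplete start date that matches the first dose's month and year (or year), or with no start date, are affected.
- A reader might infer that these events are attributed to study drug. Treatment-emergent is a timing label; causality is a separate investigator rating, and the related-event tables use it. A misdated event reaches those tables only if it is rated related or the rating is blank, which 4.12.1 treats as related.
- A reader might infer that the impossible end dates in Step 6 distort the safety results. They change no TEAE count, no AE-duration summary is planned, and listings are not imputed.

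**Conclusion.** The point holds for AEs with incomplete start dates: as written, SAP 4.12.1 counts some screening events as treatment-emergent when the recorded end date shows they resolved before any drug. The SAP already accepts the needed principle for medications. It is a minor point. The effect is at most about 5 percentage points per misclassified patient per term in an arm of 20, and less in a larger full analysis set. The total effect cannot be computed, because the documents do not say how many AE dates are incomplete; it is probably small. The conclusion assumes that an onset imputed to the first-dose day is treated as treatment-emergent.

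**What to change.** Add one sentence to SAP 4.12.1: if the known full or partial end date shows that the AE ended before the first dose of study treatment, the event is not treatment-emergent and its start date is not imputed to the first dose. The test should use the end date as recorded, not an imputed one. Where a partial end date leaves the order open (for example, an end in the month of first dose with the day unknown), the present default can stand.

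As a programming note only, an imputed end date should not be earlier than the AE start date.

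The cost is a line or two of SAP text and the matching derivation code. No new data and no protocol amendment are needed.
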